CLINICAL STUDY PROTOCOL

Study Title: **Treatment of Restless Leg Syndrome (RLS) Augmentation with Ecopipam, a D1 Specific Antagonist**

Sponsors: Houston Methodist Research Institute (HMRI)
[name].

IND #: 132835

Principal Investigator: [name].
Director of Movement Disorders Clinic
Houston Methodist Neurological Institute (HMNI)
Houston Methodist Research Institutes (HMRI)
Houston Methodist Hospital

Medical Emergencies: [name].
[contact]
Mobile [contact]

Protocol Version: V4.0 - 09.25.17

[name].
Principal Investigator/Sponsor-Investigator
Director, Movement Disorders
Houston Methodist Neurological and
Research Institutes
[name]
[name]
[contact]

Date

Table of Contents

STUDY SYNOPSIS	3
BACKGROUND AND RATIONALE FOR THE OBJECTIVES	3
STUDY AIMS/OBJECTIVES	3
STUDY DESIGN	4
PROCEDURES	
Protection of Human Subjects	5
Informed Consent and HIPAA Compliance	5
Potential Risks and Benefits	6
Statement of Non-Participation	6
Patient Confidentiality (HIPAA)	6
Eligibility (Inclusion/Exclusion Criteria)	8 7
Study Procedures	8 7-8
Schedule of Events	8
Investigational Product	8-9
Event Monitoring of Subjects	10
Data Management and Storage	11
Reporting of Study Findings	15 14
Participant Compensation	15 14
REFERENCES	12
ATTACHMENTS 1-10	13-23

STUDY SYNOPSIS

This is an exploratory study, the first ever designed specifically to treat augmentation, designed to assess gross tolerability and obtain data for a power analysis and other study design features in subsequent studies, if a signal is detected. A cross-over design was selected over an open label study specifically to blindly document the effect of D1 antagonist removal. It is not at all known if there will be a carry-over effect, immediate return of symptoms, rebound exacerbation, etc. Future studies could assess the ability to discontinue the D2 agonist, the ability to prevent augmentation in DA treated patients, and the assessment of a D1 antagonist to treat de novo RLS.

Project specific aim: (1) To determine the mechanism of dopaminergic induced augmentation and if a D1 antagonist drug can improve augmentation symptoms.

Background and Rationale for the Objectives

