Ecopipam (Psyadon Pharmaceuticals,) is a D1 specific antagonist, in fact the only D1 specific antagonist to undergo major human trials, with good CNS penetration and long T1/2 (8-15 hours). The drug has been tested in >1,000 subjects and has undergone Phase 2/3 trials for Tourette’s syndrome, obesity, schizophrenia, cocaine dependency, Lesch Nyhan disease, and diabetes mellitus. Doses range in these trials was 10-200 mg/day, but receptor saturation is thought to occur rapidly at doses of 100 mg/day. Safety profile has been good with sedation being the most common (potentially desirable in this population) adverse event.

Study Aims/Objectives

Aim 1

To determine the mechanism of dopaminergic induced augmentation and if a D1 antagonist drug can improve augmentation symptoms

Study Design

This is a double-blind, exploratory proof of concept, cross-over trial of the D1 antagonist ecopipam for subjects with augmented RLS. We prefer a cross-over compared to open label because we desire a blinded drug withdrawal. We will recruit 10 subjects taking dopamine agonists for RLS who are currently experiencing augmentation. Problematic augmentation will be assessed using the Augmentation Severity Rating Scale (ASRS). The goal is to have 8 completers. There is no power analysis as this is an exploratory study and there is no previous data on treatment of augmentation. “Meaningful improvement” is not even

established. A safety analysis will be done after 5 subjections have been enrolled by Psyaden Pharmaceuticals Inc. Duration of study and is based mostly on contracted drug availability for this pilot study.

Protection of Human Subjects

This study will be conducted in accordance with:

- Principles of the Declaration of Helsinki (revised version of Seoul, Korea, October of 2008).
- Good Clinical Practice (GCP) guidelines, as defined by the International Conference on Harmonization (ICH) Guideline, Topic E6, the United States Code of Federal Regulations, Title 21, Part 50 (21CFR50) – Protection of Human Subjects and Part 56 – Institutional Review Boards.
- Health Insurance Portability and Accountability Act (HIPAA), and all other applicable local regulatory requirements and laws.

Personnel involved in conducting this study will be qualified by education, training, and experience to perform their respective task(s) in accordance with GCP.

Informed Consent and HIPAA Compliance

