We will recruit up to 10 subjects with a goal of 8 completers. Study candidates will be screened for inclusion and exclusion criteria by any member of the study team. Those who meet criteria and consent to the study will be enrolled. If no consent provided, the patient will not be enrolled and the reason for their non-participation included with the date of screening.

Eligibility Criteria

Inclusion Criteria

- Provide consent to participate in the study
- Individuals of either sex, 21-85~~9~~ years of age
- Clinically defined Restless Leg Syndrome, and problematic augmentation currently on dopaminergic treatment.
- Subjects with reproductive capability including all males and women of child-bearing potential (WOCBP) must agree to practice continuous abstinence or adequate contraception methods (appropriate double barrier method or oral, patch, implant, or injectable contraception) from as soon as feasible during screening period until at least 30 days after the last dose (i.e., intermittent abstinence based on “rhythm”, temperature monitoring, or other means of timing is not acceptable)

Exclusion Criteria

- Current use of Opioid medications
- Clinical relevant depression or other medical problems that in the opinion of the investigator would not allow for safe completion of the protocol.
- Suicidal ideation
- History of epilepsy
- Current MAO inhibitors
- History of hepatic or renal impairment
- Women who are pregnant or breastfeeding

Study Procedures

Our aim is to determine the mechanism of dopaminergic induced augmentation and if a D1 antagonist drug can improve augmentation symptoms. Subjects will be randomized to Ecopipam or placebo for 5 weeks/arm in two periods with a 2-week washout period in between. Total time for subject participation is

approximately 13 weeks.

Medical History

The history will center on risk factors and symptoms or disorders relevant to neurological disorders.

Physical and Neurological Examinations

Brief standard neurological examinations will be done similar to that of a normal clinic visit. Laboratory assessments of serum chemistry and a 12-lead ECG will be conducted on the first day (before initiating treatment) and the last day of treatment of each crossover phase (i.e. Ecopipam or placebo).

At each Visit subjects will undergo:

- Verification of continued trial participation
- Assessment of overall wellness with query for adverse events and safety reporting

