- Clinical Global Impressions and safety calls at week 1 and 3 of each arm, and 1 week after withdrawal) of each arm.
- Completion of following instruments:
 - International RLS Rating Scale,
 - Augmentation Severity Rating Scale,
 - Epworth Sleep Scale,
 - Hamilton Depression Scale,
 - MOS Sleep Scale,
 - Fatigue Severity Scale, and
 - Montreal Cognitive Assessment
 - Columbia Suicide Assessment Scale.
 - Vital signs and examination
- Education on and/or review of the 24-hour RLS Symptom diary to be kept just prior to starting each arm and just before ending each arm. Analysis will be last observation carried forward.

Concurrent Medications for RLS

The following medications are allowed dopamine agonists (pramipexole, ropinirole, rotigotine)
The following medications are prohibited: dopamine antagonists, anti-histaminergic medications. In addition, Ecopipam has been shown a competitive inhibitor for CYP2D6 at nanomolar concentrations, and as such, the use of strong CYP2D6 inhibitors (i.e. Fluoxetine, Paroxetine, Bupropion, Quinidine, Cinacalcet and ritonavir) are prohibited.

Schedule of Events:

Study procedures (Per patient)	Baseline Screening Visit: Day -14 to 0	Visit 1: Day 0	Phone Call 1: Day 8	Visit 2: Day 15	Phone Call 2: Day 22	Visit 3: Day 36	Phone Call 3: Day 43	Visit 4: Day 50	Phone Call 4: Day 57	Visit 5: Day 65	Phone Call 5: Day 72	Visit 6: Day 84	Phone Call 6: Day 91
Informed consent	X												
Inclusion/exclusion criteria	X												
Demographic data	X												
Medical history	X												
Prior and/or concomitant medication review	X	X	X	X	X	X	X	X	X	X	X	X	X
Physical examination/Neurological exam	X			X		X		X		X		X	
Vital signs	X			X		X		X		X		X	
12-Lead ECG	X					X						X	
Urine pregnancy test (WOCBP)	X					X						X	
Serum Chemistry	X					X						X	
International RLS Rating Scale (IRLS Scale)		X		X		X		X		X		X	
Body weight and height		X		X		X		X		X		X	
Augmentation Severity Rating Scale	X	X		X		X		X		X		X	
Epworth Sleep Scale		X		X		X		X		X		X	
Hamilton Depression Scale		X		X		X		X		X		X	
MOS Sleep Scale		X		X		X		X		X		X	
Montreal Cognitive Assessment (MoCA)		X		X		X		X		X		X	
Fatigue Severity Scale		X		X		X		X		X		X	
Columbia-Suicide Severity Rating Scale (C-SSRS)		X		X		X		X		X		X	
Clinical Global Impressions (CGI)		X	X	X	X	X	X	X	X	X	X	X	X
Dispense 24-hour RLS Symptom diary	X							X					
Review of 24-hour RLS symptom diary		X		X		X		X		X		X	
Study drug dispensation		X						X					
Adverse Events		X	X	X	X	X	X	X	X	X	X	X	X

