Investigational Product

Ecopipam (also known as PSYRX 101 or SCH 39166) hydrochloride is a potent, selective antagonist of human D1 and D5 dopamine receptors. Dopamine is a neurotransmitter in the central nervous system, and its receptors have been classified into two “families” based on their genetic structure: “D1” (including subtypes D1 and D5) and “D2” (including subtypes D2, D3 and D4). D1-receptor super-sensitivity may be a mechanism for the repetitive and compulsive self-injurious behaviors. Ecopipam is a selective antagonist of the D1-receptor family and had been investigated for the symptomatic relief of self-injurious behavior (SIB) in patients with Lesch-Nyhan Disease, Pathological Gambling and Tourette Syndrome. Detailed information about ecopipam development may be found in the Investigator Brochure.

Subjects will be randomized in a double-blind fashion to study drug: ecopipam or matching placebo, supplied by Psyadon Pharmaceutical for study period 1 and 2. Prior to drug dispensation to subjects, subjects will be provided a diary, instructed on daily morning dosing, and asked to return all unused drug and packaging with the diary to the clinic. Subjects will be instructed to report any concerns and/or side effects on contact calls that will occur between study visits.

The double-blind drug assignment code will be maintained in a confidential manner where investigator, study team and patients are unaware of individual treatment assignments. Randomization process must be completed by research personnel not involved in conduct of study visits. Only in the event of a subject related emergency with the specific request to unblind the study drug by the Principal Investigator will the identity of the double-blind drug will be disclosed.

Subjects will be seen six times to complete the study. Arm1 baseline/screening, Arm 1 week 3, Arm 1 week 5, Arm 2 baseline, Arm 2 week 3, Arm 2 week 5. Once daily morning dosing will occur for 5 weeks per arm with weekly dose escalation as the example shows below:

Study Period 1

- Ecopipam or matching placebo 25 mg by mouth for 7 days (week 1), followed by
- Ecopipam or matching placebo 50 mg by mouth for 7 days (week 2), followed by
- Ecopipam or matching placebo 100 mg by mouth for 23 days (weeks 3).
- Wash-out for 2 weeks to allow subjects to switch study arms.

Study Period 2

- Matching placebo or ecopipam 25 mg by mouth for 7 days (week 7), followed by

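### Last observation carried forward, the protocol's only efficacy-analysis rule, does not suit a two-period titration crossover and would bias the treatment difference if end-of-arm values are missing

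*Protocol*

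**What the plan says.** In Study Procedures, the list of what is done at each visit ends its bullet on the 24-hour RLS symptom diary with: "Analysis will be last observation carried forward". The protocol contains no other efficacy-analysis rule. The sentence does not say which endpoints it covers or where carrying stops. The same bullet says the diary is "to be kept just prior to starting each arm and just before ending each arm".

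The design is a two-period crossover: "Subjects will be randomized to Ecopipam or placebo for 5 weeks/arm in two periods with a 2-week washout period in between". Under Investigational Product, each arm has 7 days at 25 mg, 7 days at 50 mg, and then the 100 mg step.

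The Schedule of Events places the rating scales at Day 0, Day 15 and Day 36 for period 1, and at Day 50 (Visit 4, after washout), Day 65 and Day 84 for period 2. Each arm therefore has one mid-arm scale visit.

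The Study Synopsis gives the purpose as to assess gross tolerability and "obtain data for a power analysis and other study design features in subsequent studies, if a signal is detected". Subject Screening says: "We will recruit up to 10 subjects with a goal of 8 completers".

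**The concern.** Carrying a value forward is defensible only if the last value stands in reasonably for the missing one. Here the dose rises within an arm, the treatment changes between arms, and an off-treatment visit lies between them. The last available value may therefore belong to a lower dose, to no treatment, or to the other treatment.

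The study is meant to supply inputs for a later power analysis, so a distorted treatment difference would pass straight into the next sample size. Tolerability is also under study, and Potential Risks reports more somnolence than on placebo in other conditions. Early departure could therefore depend on treatment.

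**Working it through.** The protocol states no alpha, power, effect size or SD, so there is no statistical figure of its own to reproduce. The check takes the visit calendar first and then the size of the error under stated assumptions.

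**Step 1. Dose at the mid-arm visit.**
- First dose on Day 0: 25 mg on Days 0–6, 50 mg on Days 7–13, 100 mg from Day 14. That is two 100 mg doses up to and including Day 15.
- First dose on Day 1: 100 mg from Day 15, so one dose.
- Period 2: 65 − 50 = 15 days after Visit 4, so the same position.

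The Day 15 or Day 65 score is in effect a 50 mg score. Separately, 7 + 7 + 23 = 37 dosing days does not match 5 weeks (35 days), and Visit 6 falls 84 − 50 = 34 days after Visit 4 while Visit 3 is at Day 36. Those passages must be reconciled, but Step 1 does not depend on them.

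**Step 2. What the rule puts in place of a missing end-of-arm value.**

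| Reading of the sentence | Value carried |
|---|---|
| Diary only, as its bullet describes it | Pre-treatment diary of that arm, so the change is zero |
| Scales, within an arm | Day 15 or Day 65 score from Step 1 |
| Scales, past the arm, Visit 4 attended | Off-treatment Visit 4 score |
| Scales, past the arm, Visit 4 also missing | End-of-arm score of the other treatment |

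**Step 3. Size.** Let D be the within-subject difference, with true mean d and SD 1. The share imputed is f = (10 − 8)/10 = 0.20. For a next paired trial (two-sided 5%, 80% power, both assumed), n = ((1.96 + 0.84)/dz)², where dz is the mean of D over its SD.

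*(a) Mid-arm value carried within the ecopipam arm, already showing a share r of the full effect.* Mean = d(1 − f(1 − r)); variance = 1 + f(1 − f)(d(1 − r))². At d = 0.5 the correct n is 32.

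| r | Mean, relative to truth | SD | n |
|---|---|---|---|
| 0.25 | 0.85 | 1.01 | 45 |
| 0.50 | 0.90 | 1.01 | 40 |
| 0.75 | 0.95 | 1.00 | 35 |
| 1.00 | 1.00 | 1.00 | 32 |

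If the imputed arm is placebo, and placebo response is the same at both visits, there is no bias.

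*(b) Raw period 1 score carried into period 2, so D = 0 for 2 of 10.* Mean = 0.8d; variance = 0.8 + 0.16d². The sample-size ratio is (0.8 + 0.16d²)/0.64.
- d = 0.5: SD 0.92, dz 0.436, ratio 1.31 (42 against 32 subjects).
- d = 0.8: SD 0.95, dz 0.674, ratio 1.41.
- d = 1.0: SD 0.98, dz 0.816, ratio 1.50.

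*(c) Visit 4 score carried into period 2.* Assume a true effect of 0.5 and a placebo response of 0.3. The eight completers contribute 0.8 × 0.5 = 0.40.
- Both incomplete subjects had placebo first: each contributes −0.3, giving 0.40 + 0.2 × (−0.3) = 0.34.
- Both had ecopipam first: each contributes 0.8, giving 0.40 + 0.2 × 0.8 = 0.56.
- The same with a rebound of 0.5 after withdrawal: each contributes 1.3, giving 0.40 + 0.2 × 1.3 = 0.66.

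Simulation (40,000 runs of 10 subjects) gave the same three means. The true value is 0.50, so the error can go either way.

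**The case against.** **Cross-period carrying is not stated.** A reader might infer that the plan copies one treatment's value into the other's period, forces the difference to zero, and so makes the next trial 31% to 50% too large. The text permits this but does not say it. Visit 4, where all scales are collected, would often supply an off-treatment value instead. The zero difference also applies only to raw scores. With change from each arm's baseline, a subject lost in washout would have a period 2 change of zero and a difference equal to plus or minus the whole period 1 change. The 31% to 50% range belongs to case (b) alone.

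**The scope is unclear.** The sentence sits in the diary bullet and may not reach the IRLS or the ASRS. The schedule lists diary review at Visits 2 and 5, so mid-arm diary entries may exist. CGI is also taken by phone on Day 22, about a week into the 100 mg step, so it escapes part of the dose argument. These points stand, but none of the readings in Step 2 makes the rule suitable.

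**Non-completion is not predicted.** Eight completers from up to ten recruits is a goal. Two incomplete subjects is an illustration, and with none the rule changes nothing.

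**The study is small and exploratory.** The sample size rests on drug availability. With n = 10 the standard error of the mean difference is 1/√10 ≈ 0.32 SD, and a 95% interval for the SD runs from about 0.69 to 1.83 times the estimate. The shifts above lie inside that noise. This lowers the severity. It does not justify adding an avoidable bias to an already imprecise estimate.

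**A statistical analysis plan might settle it.** None is shown. The point is not missing detail, because any such plan would have to follow the protocol's sentence or contradict it.

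**Conclusion.** The point holds in conditional form. The stated rule is unsuited to this design on every reading considered, and it would bias the treatment difference for subjects without an end-of-arm value. With 2 of 10 incomplete, carrying within the ecopipam arm gives about 0.85 to 0.95 of the true mean when the mid-arm value shows 25% to 75% of the full effect. Carrying raw period 1 scores gives 0.80. Carrying Visit 4 scores gives 0.34 to 0.66 against a true 0.50. All effect sizes, placebo responses and shares are assumptions, since the protocol supplies none.

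It would go too far to say that the estimates will be biased, that the bias must shrink the effect, or that the SD is badly distorted. Carrying within an arm leaves the SD almost unchanged; case (b) lowers it by about 8% at d = 0.5. For a ten-subject exploratory study this is a should-fix.

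**What to change.** Replace the sentence with:

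> Observed data are analysed without carrying values forward, by a linear mixed model with treatment, period, sequence, visit and treatment-by-visit as fixed effects and subject as a random effect; the treatment contrast is taken at the end-of-arm visit. No value is carried from a pre-arm, washout or other-period visit.

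The visit terms are needed. Without them the treatment effect would average near-50 mg mid-arm scores with end-of-arm scores for every subject.

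Take the effect and SD for the next trial from this model. Show the completers' paired differences alongside, not in its place, because completers are a selected group. Keep carrying forward within an arm at most as a sensitivity analysis, and name the endpoints it covers.

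The cost is one protocol sentence and routine code, with no new data. Intervals will be slightly wider, and the model has few degrees of freedom at n = 10. If it does not fit, analyse the end-of-arm values only, with treatment, period and sequence terms.

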- Matching placebo or ecopipam 50 mg by mouth for 7 days (week 8), followed by
- Matching placebo or ecopipam 100 mg by mouth for 23 days (week 9).

Subjects will be allowed to reduce to a previous tolerated dose if needed. All other RLS medicines will remain stable.

IMP preparation blinding

Principal Investigator and study staff will handle the study drug and supplies in accordance with the protocol and GCP guidelines.

IMP receipt

1. Investigational drugs will be sent directly to Movement Disorders Clinic to the attention of the Principal Investigator. Upon receipt of IMP, the research staff will inventory these drugs at the time of receipt in the clinic to determine that they have been received in good condition and that the information on the packing slip matches exactly what has been sent. Any discrepancies will be promptly brought to the attention of the sponsor/supplier.
2. Principal Investigator (PI) will be notified of drug receipt. With knowledge of what is known about drug's toxicity, potency, sensitising potential and risk of cross-contamination, PI or delegate will visually inspect bulk IMP, verify its receipt in good condition and recommend packaging instructions per site SOP.
3. All appropriate follow-up required per drug sponsor will be completed.
4. All documentation accompanying or detailing the delivery are noted and filed in the Regulatory binder. This may include package inserts, certificates of compliance with GMP Guidelines, certificates of analysis (test products), or product release certificates (reference products). If any expected documents are missing, a designee must notify the Drug Sponsor without undue delay.
5. Drug will be stored in a temperature monitored locked cabinet in a limited access location.

IMP labeling

1. Study team member appropriately trained on GCP requirements and study protocol will complete IMP labelling
2. Another appropriately trained member of the team will review the labels before printing.
3. Label will include Kit ID, patient ID/randomization #/code, study drug name (i.e. PSYRX101 or matching placebo), dose, instructions on use and the following statement: "Caution: New Drug-Limited by Federal law to investigational use"
4. An unblinded study team member (or packager) is responsible for assigning computer generated randomization schedule to study patients.

5. Packaging area is appropriately cleaned, windows and doors closed, and extraneous materials removed.

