During the study, the Investigator and study team will be responsible for monitoring, collecting, following-up on, and reporting AEs and SAEs, as detailed in this section of the protocol. Adverse events will be reported by the subject (or, when appropriate, by a caregiver, surrogate, or the subject's legally acceptable representative) according to the definition below. Only adverse events associated with the research component of trial participation will be captured, examples include but are not limited to: somnolence, headache, insomnia.

The stopping rules for this trial will be determined by the Sponsor Investigator, Houston Methodist Hospital &/or Houston Methodist Research Institute, and/or HMRI Institutional Review Board. The Principal Investigator may withdraw a subject for their safety and welfare. Participants will be withdrawn at either 3x ULN for AST/ALT, kidney function changes from baseline as determined by BUN/Creatinine or when unintended pregnancy occurs.

Event Monitoring Definitions

Adverse Event (AE): An adverse event (AE) is any untoward medical occurrence associated with the use of a drug in humans, whether or not considered drug related. An adverse event can therefore be any unfavorable and unintended sign (including an abnormal laboratory finding), symptom, or disease temporally associated with the use of a drug and does not imply any judgment about causality. An adverse event can arise with use of any drug or medicinal product. AEs are to be reported to the IRB per IRB policy and to the sponsor at the time of annual reporting.

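### Ecopipam is described as a CYP2D6 inhibitor, yet no rule is aimed at co-administered CYP2D6 substrates, the drugs this property directly affects (minor safety point)

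*Protocol*

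**What the plan says.** The Protocol has one CYP2D6 rule, under Concurrent Medications for RLS: "Ecopipam has been shown a competitive inhibitor for CYP2D6 at nanomolar concentrations, and as such, the use of strong CYP2D6 inhibitors" are prohibited, followed by six named drugs. The same section allows three dopamine agonists and prohibits dopamine antagonists and anti-histaminergic drugs. Exclusion Criteria adds current opioids and current MAO inhibitors, with no mention of CYP2D6.

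The other provisions that could bear on a subject's background medication are general:

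- Exclusion Criteria: "Clinical relevant depression or other medical problems that in the opinion of the investigator would not allow for safe completion of the protocol".
- Investigational Product, after the dosing steps: "All other RLS medicines will remain stable". Step-down to an earlier tolerated dose is also allowed.
- Safety Monitoring of Subjects: "The Principal Investigator may withdraw a subject for their safety and welfare", together with withdrawal rules for liver enzymes, kidney function and pregnancy.
- Study Design: "A safety analysis will be done after 5 subjections have been enrolled".
- Schedule of Events: a medication review at every visit and call.

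For further background on the drug, Investigational Product refers the reader elsewhere: "Detailed information about ecopipam development may be found in the Investigator Brochure".

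**The concern.** The protocol starts from a property of ecopipam as perpetrator: it inhibits CYP2D6. The drugs which that property puts at risk are those that CYP2D6 clears, because their concentrations rise while ecopipam is on board. The rule actually drawn bars other inhibitors. That protects against a different problem, namely added inhibition or a rise in ecopipam itself if CYP2D6 clears it.

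Followed as written, the protocol therefore lets a subject on a sensitive CYP2D6 substrate enter and escalate to 100 mg daily with no required look at that drug's dose, unless an investigator happens to use general discretion. What is at stake is the safety of any such subject. No efficacy rating is called into question.

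**Working it through.** **1. Is any rule aimed at substrates?** Set against the stated property, each rule reads as follows.

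| Protocol section | Rule | Aimed at CYP2D6 substrates? |
|---|---|---|
| Concurrent Medications for RLS | Strong CYP2D6 inhibitors barred | No |
| Concurrent Medications for RLS | Dopamine antagonists, anti-histaminergics barred | No; may catch some incidentally |
| Exclusion Criteria | Opioids, MAO inhibitors | No; may catch some incidentally |
| Exclusion Criteria | Investigator's judgement on medical problems | No; does not name co-medication |
| Investigational Product | Stable RLS medicines | No; RLS medicines only |
| Potential Risks; Safety Monitoring of Subjects | Risks listed; withdrawal rules | Interaction not mentioned |
| Schedule of Events | Medication review, 13 contacts | No criterion or action attached |

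**2. How long is the exposure?** About 5 weeks per period; the exact figure depends on the section. The dosing steps give 7 + 7 + 23 = 37 days. The stated 5 weeks per arm is 35 days. The schedule gives 36 days in period 1 (Day 0 to Day 36) and 84 − 50 = 34 days in period 2.

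**3. How soon would a problem be seen?** Visit 2 (Day 15) and Visit 5 (Day 65) fall at the step-up to 100 mg. In the schedule, one phone call follows (Day 22 or Day 72). The next vital signs and ECG come 36 − 15 = 21 days later in period 1 and 84 − 65 = 19 days later in period 2. A check before entry is therefore worth more than later detection.

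**4. How large could the rise be?** The protocol gives none of the inputs, so these are assumptions. For reversible inhibition,

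AUC ratio = 1 / [fm/(1 + I/Ki) + (1 − fm)],

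where fm is the fraction of the substrate cleared by CYP2D6 and I/Ki is the inhibitor concentration relative to its inhibition constant. I/Ki is taken as proportional to dose, so its values at 25 and 50 mg are 0.25 and 0.5 of the value at 100 mg. Example: fm 0.9 and I/Ki 1 give 1/(0.45 + 0.10) = 1.82.

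| fm | I/Ki at 100 mg | 25 mg | 50 mg | 100 mg |
|---|---|---|---|---|
| 0.9 | 0.1 | 1.02 | 1.04 | 1.09 |
| 0.9 | 1 | 1.22 | 1.43 | 1.82 |
| 0.9 | 10 | 2.80 | 4.00 | 5.50 |
| 0.5 | 0.1 | 1.01 | 1.02 | 1.05 |
| 0.5 | 1 | 1.11 | 1.20 | 1.33 |
| 0.5 | 10 | 1.56 | 1.71 | 1.83 |

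The range runs from negligible to large, and nothing in the protocol says where in it this trial lies.

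**5. Does the effect outlast the period?** The Background section gives a half-life of 8 to 15 hours. Five half-lives are 40 to 75 hours (1.7 to 3.1 days). The 14-day washout is 336 hours, or 336/15 = 22.4 to 336/8 = 42 half-lives. Reversible inhibition would be gone well before period 2.

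**The case against.** The strongest answer is that no harm is shown. The hazard needs two conditions: inhibition that matters at 100 mg daily, and a subject who takes a substrate. The protocol's phrase about nanomolar concentrations gives neither a constant nor a plasma level. The Background section reports more than 1,000 subjects treated at 10 to 200 mg daily, up to twice this trial's top dose, with a good safety profile. Potential Risks says that only somnolence exceeded placebo. The Investigator Brochure may contain interaction data, and a substrate restriction may have been considered and judged unnecessary. Medication is already reviewed at screening and on Day 0, so the pre-entry procedure exists.

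Most of this stands as a limit on importance. It does not fill the gap. Earlier experience does not show that substrate users were included or how their drugs were handled, and a medication review without a criterion does not tell staff what to look for. The safety analysis is triggered by enrolment of 5 subjects, not by exposure at 100 mg or by co-medication.

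A reader might also infer that the ban on strong inhibitors is itself an error. The document does not support that. The ban is sensible if inhibition adds up or if CYP2D6 clears ecopipam, and nothing elsewhere contradicts it. The point concerns only the rule that is absent beside it.

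**Conclusion.** The point holds as a minor safety matter. The textual gap is certain: the protocol has one CYP2D6 rule, aimed at strong inhibitors, and none aimed at substrates. Its clinical importance is unknown. The AUC ratios at 100 mg, from 1.05 to 5.50, rest wholly on assumed I/Ki (0.1 to 10), assumed fm (0.5 or 0.9) and assumed dose-proportional concentrations. With 10 subjects, it is possible that none takes a sensitive substrate.

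Two stronger readings are tempting and are not supported. One is that subjects will come to harm; the document has no figure from which to conclude this. The other is that the interaction biases the treatment comparison or carries over into period 2. Nothing in the protocol links the interaction to an efficacy rating, and the washout is far longer than reversible inhibition would last.

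**What to change.** In the Concurrent Medications for RLS paragraph, add:

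- CYP2D6 substrates with a narrow therapeutic index are prohibited.
- Other sensitive CYP2D6 substrates require a documented dose review before randomisation. The dose is not adjusted by period, because treatment is blinded.
- No such substrate may be newly started during either treatment period.
- Compliance is checked at the medication review already scheduled at each contact.

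A short list of named drugs, as the protocol already gives for inhibitors, would make the rule easy to apply; the investigator should draw it up with the Investigator Brochure at hand.

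The cost is a few sentences and no new procedure. The downside is that a few candidates may need a review or be excluded, in a pilot with 10 places and a target of 8 completers.
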